### 6.1.2 Randomisation (Telephone Call)

Randomisation will occur upon confirmation of eligibility. The Investigator will follow the randomisation procedure (IRT), as described in Section 3.4, and inform the subject of treatment allocation (GT005 or untreated control).

For subjects randomised to the untreated control, Day 1 will be defined as the day following randomisation for the calculation of Week 5 to 96 visits.

For subjects randomised to GT005, the day of surgery is described as Day 1 in the study timeline (Section 6.1.3). The interval between randomisation and Day 1 must be sufficient to allow arrangements to be made for surgery, and to prepare the subject, as appropriate, for treatment. Randomisation therefore resides within the interval between screening and surgery, which should not exceed 8 weeks, unless agreed by the Sponsor Medical Monitor, who may approve an extension for up to a maximum of 12 weeks.

The Investigator will ask the subject if any changes have occurred since the screening visit and record in the eCRF:

- AEs
- Concomitant medication

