#### 6.1.3.2 Surgery – Day 1 (Surgical Site)

##### Deferred GT005 Delivery

In the event the GT005 administration is deferred during the surgical procedure (e.g., due to an AE occurring during surgery) the administration surgery may be rescheduled within 10 weeks of the original surgery date if agreed by the Sponsor Medical Monitor. Additionally, if the time from screening is extended past 12 weeks, in case of GT005 deferral, FAFs will be repeated, in addition to standard ophthalmic examination, haematology and biochemistry, and visual acuity (BCVA and LLVA).

The following assessments are required during surgery:

- [REDACTED]
- AEs
- Concomitant medications
- [REDACTED]
- [REDACTED]
- [REDACTED]

The procedure for the administration of GT005 is described in Section 5.4 and in the Surgical Manual.

■ [REDACTED]  
■ [REDACTED]  
■ [REDACTED]

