### 2.1.1.2 Baseline and post-Baseline

*Baseline* (Day 1) is defined as

- the day following randomization for subjects randomized to untreated control
- the day of successfully receiving GT005 administration for subjects randomized to GT005
- or the latest surgery date for subjects who were randomized to GT005 but failed to receive GT005 administration on the first attempt to surgery (if applicable)

The baseline value for efficacy and safety variables is the last available value (scheduled or unscheduled) collected prior to the date of *Baseline*, or on the date of *Baseline* but prior to the time of GT005 administration for GT005 treatment groups.

All data collected after the date of *Baseline* are defined as post-baseline. The *study day* for a baseline or post-baseline scheduled or unscheduled visit is defined as:

$$\text{Study day} = \begin{cases} (\text{Date of visit}) - (\text{Date of randomization}) & \text{Untreated} \\ (\text{Date of visit}) - (\text{Date of treatment administration}) + 1 & \text{GT005} \end{cases}$$

The *study day* for a scheduled or unscheduled visit before baseline is defined as

$$\text{Study day} = \begin{cases} (\text{Date of visit}) - (\text{Date of randomization}) - 1 & \text{Untreated} \\ (\text{Date of visit}) - (\text{Date of treatment administration}) & \text{GT005} \end{cases}$$

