### 2.6.1 Secondary endpoint(s)

The corresponding secondary endpoints are:

1. Change from baseline through Week 96 in GA area as measured by FAF
2. Frequency of treatment emergent adverse event (AE) through Week 96
3. Change in retinal morphology on multimodal imaging through Week 96
- 4.a Change in best corrected visual acuity (BCVA) Score via the early treatment for diabetic retinopathy (ETDRS) chart through Week 96
- 4.b Change in low luminance difference (LLD) via the ETDRS chart through Week 96
- 5.a Change in reading performance as assessed by Minnesota low-vision reading test (MNRead) chart through Week 96
- 5.b Change in functional reading independence (FRI) index through Week 96
6. Change in quality of life measured on the visual function questionnaire-25 (VFQ-25) through Week 96

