## **2.7 Safety analyses**

For all safety analyses, the FAS will be used. All listings and tables will be presented by the treatment group.

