### **2.7.1 Adverse events (AEs)**

Only AEs that occurred during the study period (from the date of randomization to the end of study) will be summarized. AEs recorded after screening but before the date of randomization will be listed only.

**Treatment-emergent Adverse Event (TEAE):** An adverse event is considered treatment emergent if the start date/time of the event is on or after the date of randomization, irrespective of the treatment arm. The primary summaries of AEs will be based on TEAEs.

The number (and percentage) of subjects with AEs will be summarized separately for ocular (study eye and fellow eye) and non-ocular events by treatment group in the following ways unless otherwise specified:

- Overall summary of death, subjects with any AE, any severe AE, any study treatment-related AE, any surgical procedure related AE, any AE leading to study discontinuation, any serious AE (SAE), any study treatment-related SAE, any surgical procedure related SAE, any SAE leading to study discontinuation
- AEs by primary SOC and PT
- AEs related to study treatment by SOC and PT (separately for study eye and non-ocular)
- AEs related to surgical procedure by SOC and PT (separately for study eye and non-ocular)
- SAEs by primary SOC and PT

- SAEs related to study treatment by SOC and PT (separately for study eye and non-ocular)
- SAEs related to surgical procedure by SOC and PT (separately for study eye and non-ocular)

A subject with multiple adverse events within a primary SOC is only counted once towards the total of the primary SOC.

All AEs, deaths, and SAEs (including those from the pre- and post-treatment periods) will be listed and those collected after the use of alternative GA therapies/medications, or during the pre-treatment, post-study period will be flagged. In addition, subjects who are not receiving treatment due to surgical procedure-related AEs will be listed separately by treatment group.

The MedDRA version used for reporting the AEs will be described in footnote.

For the legal requirements of ClinicalTrials.gov and EudraCT, two required tables on “on-treatment/treatment emergent” adverse events which are not serious adverse events with an incidence greater than 2% (or other cutting point as appropriate) and on “on-treatment/treatment emergent” serious adverse events and SAE suspected to be related to study treatment will be provided by system organ class and preferred term on the safety set population (i.e., the FAS of this study).

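### Treatment-emergent AEs are counted from randomisation, so all-cause GT005 tables include pre-surgery events and, for subjects reaching Week 96, a modestly longer window than control

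*SAP*

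**What the plan says.** The secondary safety endpoint in SAP 2.6.1 is "Frequency of treatment emergent adverse event (AE) through Week 96". SAP 2.7.1 supplies the definition: "An adverse event is considered treatment emergent if the start date/time of the event is on or after the date of randomization", whatever the arm. It adds that "Only AEs that occurred during the study period (from the date of randomization to the end of study) will be summarized" and that "The primary summaries of AEs will be based on TEAEs". SAP 2.7 sets the population: "For all safety analyses, the FAS will be used". The planned output is numbers and percentages of subjects; no exposure-adjusted rate is described.

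The visit clock is arm-specific. Protocol 6.1.2 counts control visits from the day after randomisation, whereas "For subjects randomised to GT005, the day of surgery is described as Day 1 in the study timeline". SAP 2.1.1.2 agrees: Day 1 is the day after randomisation for control and "the day of successfully receiving GT005 administration for subjects randomized to GT005". The same protocol section places randomisation inside the screening-to-surgery interval, which is limited to 8 weeks, or 12 with Medical Monitor approval.

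SAP 2.7.1 does flag events from a pre-treatment period, but only in listings. It does not say whether that period ends at randomisation or at surgery.

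**The concern.** A subject allocated to GT005 waits for surgery after randomisation. Until then neither vector nor operation has been received, so an event in the wait cannot be a consequence of either. Under SAP 2.7.1 it still enters the main GT005 tables as treatment-emergent. Control has no equivalent period: its follow-up clock starts one day after randomisation.

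Two things are at stake. One is labelling: the all-cause AE and SAE tables, and the registry tables built on the same flag, present some pre-surgery events as emerging on treatment. The other is comparability. If one arm is observed for longer and only percentages of subjects are shown, its percentage rises even when the underlying event rates are equal. Ascertainment during the wait also differs. GT005 subjects have a pre-surgery AE review and an ocular safety check (Protocol 6.1.3.1 and 7.3.2), while the next scheduled contact for control after the randomisation call is the Week 5 telephone call (Protocol Table 2).

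**Working it through.** **Inputs**
- TEAE start, both arms: randomisation (SAP 2.7.1).
- Week 96 clock: randomisation + 1 day for control; surgery or administration for GT005 (Protocol 6.1.2, SAP 2.1.1.2).
- Follow-up: 96 weeks in both arms (Protocol 3.5).
- Screening to surgery: up to 8 weeks, or 12 with approval (Protocol 6.1.2).
- Wait from randomisation to surgery, *g* weeks: not given. Assumed range 2 to 12. Because the 8- and 12-week limits run from screening, they are ceilings for *g*.

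**Step 1. The plan's own total.** The Protocol synopsis gives 104 weeks of participation: 8 + 96 = 104. Reproduced.

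**Step 2. Window from randomisation to Week 96.**
- Control: (96 × 7 + 1)/7 = 96.14 weeks.
- GT005: 96 + *g* weeks.
- Difference: *g* weeks minus 1 day.

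**Step 3. Size.** The last column assumes the same constant hazard in both arms and a control incidence of 30% (an assumption), so GT005 incidence = 1 − 0.70^((96 + *g*)/96.14).

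| Wait *g* (weeks) | GT005 window (weeks) | Excess over control | Pre-surgery share, *g*/(96 + *g*) | GT005 incidence with no drug effect |
|---|---|---|---|---|
| 2 | 98 | 1.9% | 2.0% | 30.5% |
| 4 | 100 | 4.0% | 4.0% | 31.0% |
| 8 (ceiling) | 104 | 8.2% | 7.7% | 32.0% |
| 12 (ceiling with approval) | 108 | 12.3% | 11.1% | 33.0% |

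With an assumed control incidence of 10%, the GT005 figure at 4 and 8 weeks is 10.4% and 10.8%; with 50%, it is 51.4% and 52.8%.

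**Step 4. Subjects stopped before Week 96.** SAP section 1 says the study is being terminated early. If a subject is stopped by a common calendar date *T* weeks after randomisation, the window from randomisation is *T* in either arm and does not depend on *g*. The length difference disappears, but GT005 events in the first *g* weeks are still labelled treatment-emergent.

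**Step 5. Counting from first surgery instead.** For subjects reaching Week 96 without a deferral, both windows are 96 weeks (ratio 1.00). For subjects stopped at *T*, the GT005 window becomes *T* − *g* and the control window *T* minus 1 day, so percentages alone would then favour GT005. This is why exposure-adjusted rates belong with the table.

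**The case against.** The case for the randomisation anchor is reasonable. It is applied explicitly to both arms, matches the all-randomised safety population, cannot hide a GT005 event, and keeps harms of a failed first operation in the main table. Treatment-related and surgery-related events have their own tables. Concomitant medication (SAP 2.4.2) and partial AE dates (SAP 5.1.1.2) are also anchored at randomisation, so it would be wrong to infer that AEs alone are on a separate clock.

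Much of this limits the size of the point and shapes the remedy. It does not remove the point. A common start makes the windows comparable only with a common stop, and for subjects reaching Week 96 the stops differ. A flag in a listing does not change a table.

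Three stronger readings are tempting but unsupported.

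- **Adding the deferral to the wait.** The protocol says "the administration surgery may be rescheduled within 10 weeks of the original surgery date if agreed by the Sponsor Medical Monitor", and 12 + 10 = 22 weeks would make the window about 23% longer. Those 10 weeks should not be read as untreated time. The deferral arises during an operation, so events after it may be surgical.
- **A longer window for every GT005 subject.** Early termination confines the length difference mainly to those who reach Week 96.
- **Simply moving the flag to Day 1 of SAP 2.1.1.2.** That Day 1 is the successful administration, or the latest surgery after a failed first attempt. Adverse events of an aborted first operation would leave the main table, and GT005 subjects who never have surgery would have no start date, although they remain in the FAS and may stay in the study (Protocol 4.3).

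**Conclusion.** The point holds for the all-cause AE and SAE tables and for any registry or AESI table built on the same flag. GT005 events between randomisation and first surgery are labelled treatment-emergent although nothing had been administered. This applies to any GT005 subject with a wait, including those affected by early termination.

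The window-length effect is modest and, where it exists, runs in one direction: it raises GT005 percentages relative to control. For subjects reaching Week 96 it is about 2% extra time at a 2-week wait, 4% at 4 weeks, at most 8% under the standard limit and 12% under the approved extension. The actual wait is not in the documents, and the incidence figures rest on an assumed constant, equal hazard and an assumed control incidence. Tables restricted to treatment-related or surgery-related events should change little, because events before surgery are unlikely to be judged related. The definition should be changed before final database lock; it does not undermine the safety analysis as a whole.

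**What to change.** In SAP 2.7.1, define treatment-emergent as onset, through Week 96, on or after:
- the start of the **first** surgery attempt, for GT005 subjects who are operated on, so that adverse events of an aborted first operation stay in the main table;
- the day following randomisation, for control and for GT005-randomised subjects who never have surgery.

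Show GT005 events from randomisation to first surgery in a separate, adjacent pre-surgery column. Apply the same flag to the SAE, AESI and registry tables.

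In SAP 5.1.1.2, use first surgery as the reference date when imputing partial AE start dates for operated GT005 subjects. Otherwise an event known only by a year equal to the randomisation year is imputed to the day after randomisation and would fall into the pre-surgery column even if it followed surgery. Where the event is known to have ended between randomisation and first surgery, keep randomisation as the reference so that it stays in that column.

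If the sponsor prefers to keep the randomisation anchor as primary, provide this table as a supplement. Either way, give exposure-adjusted rates with it. They handle follow-up cut short by termination, and the few deferred subjects whose window from first surgery could reach 96 + 10 = 106 weeks if Week 96 is counted from the successful administration.

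The cost is a small amount of extra programming: one flag, one column, and the imputation reference date. Pre-surgery events move out of the main GT005 column but remain visible beside it, and no data are lost.

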#### 8.4.2 Causality Assessment

The relationship of an AE to IMP or surgical procedures will be classified by the Investigator or medically qualified designee.

When assigning relatedness of the AE, consideration will be given to whether there is a plausible relationship to either the IMP or the surgical procedure.

The following are definitions of relatedness that will be used in this study:

- Related: reports including good reasons and sufficient information (e.g., plausible time sequence, dose-response relationship, pharmacology, positive de-challenge and/or re-challenge) to assume a causal relationship to the IMP or the surgical procedure. In the sense that it is plausible, conceivable or likely
- Not related: reports including good reasons and sufficient information (e.g., implausible time sequence and/or attributable to concurrent disease or other drugs) to rule out a causal relationship to the IMP or the surgical procedure with IMP administration
- Unknown: there is insufficient information to assess plausibility of causal relationship to the IMP or the surgical procedure

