### 9.4.3 Safety Assessments

Safety evaluations include AEs, ophthalmic imaging and examinations, BCVA (ETDRS) score (assessed as both an efficacy and safety endpoint), vital signs, laboratory safety (biochemistry and haematology), [REDACTED]

AEs will be summarised in two parts: systemic events and ocular events. For systemic events, data will be displayed according to treatment received (low dose [REDACTED] vg, high dose [REDACTED] vg, and untreated). Ocular events will be displayed according to treatment allocation (including GT005 dose group) and study eye (study eye and contralateral eye).

All AEs (overall, by seriousness, by severity, by relationship) recorded throughout the study will be reported following classification according to the Medical Dictionary for Regulatory Activities (MedDRA) dictionary. [REDACTED]

Systemic safety evaluations including vital signs, laboratory safety, [REDACTED] will be summarised over time by dose and overall.

Ocular safety evaluations including ophthalmic examination variables (cataract grading, intra-ocular pressure, etc.) and BCVA scores will be summarised in the same manner as ocular efficacy variables, dependant on data type.

[REDACTED]  
[REDACTED]  
[REDACTED]  
[REDACTED]  
[REDACTED].

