### 1.2.1 Primary estimand(s)

The primary estimand will focus on the effect attributable to different doses of GT005 on GA change on FAF at Week 48 in subjects who have not received alternative GA medications or therapies in the study eye.

The primary estimand is described by the following attributes:

1. **Population:** Subjects with GA secondary to AMD. Details on the target population are defined by the study inclusion and exclusion criteria.
2. **Variable:** Change from baseline in GA lesion size (mm^2) based on FAF at Week 48
3. **Treatment:** The randomized treatment (different doses) of the investigational therapy GT005 delivered through transvitreal subretinal injection.
4. **Summary Measure:** The treatment difference of the variable means between GT005 and untreated control, represented as % relative to untreated control.
5. **Intercurrent events and data handling strategy:** defined in [Table 1-2](#).

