If for the same subject, several consecutive AEs (irrespective of study treatment causality, seriousness and severity) occurred with the same SOC and PT:

[figure not shown]
- a single occurrence will be counted if there is  $\leq 1$  day gap between the end date of the preceding AE and the start date of the consecutive AE
- more than one occurrence will be counted if there is  $> 1$  day gap between the end date of the preceding AE and the start date of the consecutive AE

For occurrence, the presence of at least one SAE /SAE suspected to be related to study treatment / non-SAE has to be checked in a block e.g., among AE's in a  $\leq 1$  day gap block, if at least one SAE is occurring, then one occurrence is calculated for that SAE.

The number of deaths resulting from SAEs suspected to be related to study treatment and SAEs irrespective of study treatment relationship will be provided by SOC and PT.

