### **2.7.1.1 Adverse events of special interest / grouping of AEs**

An AESI (serious or non-serious) is one of scientific and medical concern specific to the Sponsor's product or program, for which ongoing monitoring and rapid communication by the Investigator to the Sponsor can be appropriate. AESIs should also be assessed as to whether it fits the criteria of an SAE and reported appropriately. AESI should be reported as per reporting requirements [Protocol Section 8.3].

The number and percentage of subjects with AESIs will be summarized separated for ocular (study eye and fellow eye) events by category, PT, and treatment groups. In addition, AESIs related to the study treatment and/or surgical procedure will be summarized by category, PT and treatment groups.

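### The registry's related-SAE subset and the related-death count are worded on study treatment alone, so events attributed only to the subretinal surgery fall outside both

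*SAP*

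**What the plan says.** SAP section 2.7.1 carries two causality attributes, study treatment and surgical procedure. Each has its own rows in the overall summary and its own AE and SAE tables by SOC and PT.

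Two outputs in the same section name only the first attribute:

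- The registry table covers all treatment-emergent SAEs and a related subset, in the SAP's words "serious adverse events and SAE suspected to be related to study treatment". The subset is defined on study treatment only: "SAE suspected to be related to study treatment will be provided by system organ class and preferred term on the safety set population".
- The death counts by SOC and PT are: "The number of deaths resulting from SAEs suspected to be related to study treatment and SAEs irrespective of study treatment relationship".

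Other places in the documents combine the causes, or include the surgery in the treatment:

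- SAP 2.7.1.1: "AESIs related to the study treatment and/or surgical procedure will be summarized by category, PT and treatment groups".
- Protocol 8.4.2 defines a related event as one with good reasons "to assume a causal relationship to the IMP or the surgical procedure".
- SAP 1.2.1 gives the estimand's treatment as "The randomized treatment (different doses) of the investigational therapy GT005 delivered through transvitreal subretinal injection".

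On eyes, the four related-event tables in SAP 2.7.1 (AE and SAE, each by treatment and by procedure) leave out the fellow eye. The first of them reads "AEs related to study treatment by SOC and PT (separately for study eye and non-ocular". Protocol 9.4.3 says: "Ocular events will be displayed according to treatment allocation (including GT005 dose group) and study eye (study eye and contralateral eye".

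**The concern.** The randomised comparison is GT005 plus an operation against nothing, because controls receive no treatment (protocol 5.4). Protocol 1.6.1.2 lists the foreseeable surgical risks, including inflammation, persistent retinal detachment, cataract, raised intraocular pressure and worsening of vision. Serious events due to the operation and not the vector are therefore to be expected as a category.

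The registry entry is what most outside readers will see. If its related subset rests on the vector alone, the related-SAE figure for GT005 omits harm that the protocol's own causality definition would call related. The related-death figure has the same gap. The SAP also leaves *study treatment* undefined for causality, so two programmers could produce different related counts from the same data.

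**Working it through.** The plan states no figure on this point, so the check is textual, with one piece of set arithmetic.

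**Step 1: what study treatment means in 2.7.1.** The overall summary lists treatment-related and procedure-related events as separate rows, for AEs and again for SAEs, and the SOC/PT tables repeat the split. SAP 2.7.1.1 joins the two with *and/or*. If study treatment already contained the surgery, the split rows would overlap by construction and the *and/or* would be redundant. The consistent reading is that study treatment here means GT005 without the operation. This is an inference, since the SAP gives no definition.

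**Step 2: follow one event.** Take an SAE in a GT005 subject that the investigator attributes to the operation and not to GT005.

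| Output | Does the event appear as related? |
|---|---|
| Overall summary (2.7.1) | Yes, in the procedure-related rows |
| Procedure-related AE and SAE tables (2.7.1) | Yes, if study eye or non-ocular |
| Related AESIs (2.7.1.1) | Yes, if it is an AESI |
| Registry table, all SAEs | Shown, without attribution |
| Registry table, related subset | No |
| Deaths from related SAEs, if fatal | No |
| Deaths from SAEs regardless of relationship, if fatal | Shown, without attribution |

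The two *No* rows are the defect. The clearest case is an operation abandoned before delivery. Protocol 6.1.3.2 foresees deferral because of an AE during surgery, and SAP 2.7.1 lists subjects left untreated because of procedure-related AEs. These subjects are in the FAS, which is the safety population. If GT005 was never delivered, an SAE that stopped the operation cannot be due to the vector, so on this reading it cannot enter the related subset.

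**Step 3: can a combined figure be recovered?** In one GT005 arm, let T be the number of subjects with a treatment-related SAE, S the number with a procedure-related SAE, and B the number with both.

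- Combined count = T + S − B, which lies between max(T, S) and T + S.
- Increase over the narrow count = S − B, which lies between max(0, S − T) and S.

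The planned tables give T and S but not B, so the combined count is only bounded. It could be rebuilt from the listings, but not from the tables or the registry.

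An illustration of the arithmetic only, with assumed rates: per 100 subjects take T = 2 and S = 5. The combined count is max(2, 5) = 5 up to 2 + 5 = 7, against 2 on the narrow definition. If S = 0, nothing changes. Nothing in the documents says where in such a range the study would fall.

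**Step 4: fellow eye.** The default in 2.7.1 reports study eye, fellow eye and non-ocular events separately unless otherwise specified. The four related-event bullets specify otherwise and drop the fellow eye. A related fellow-eye event is then counted in the overall summary's related rows and within the all-cause AE or SAE tables. It has no related table by PT unless it is an AESI. SAP section 4 does not mention the restriction.

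**The case against.** The strongest reply is that the harm question is answered by comparing all SAEs between arms, not by investigator attribution, and that this comparison is fully planned. All SAEs and all deaths are tabulated by treatment group, and surgery-related AEs and SAEs have their own tables. This stands. A reader might infer from the two narrow outputs that surgical harm is reported as unrelated throughout, and the documents do not support that. The gap is confined to the registry's related subset and the related-death count.

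The reply can also say that *study treatment* is undefined for causality. The estimand, protocol 8.4.2 and SAP 2.4.1, which summarises surgery under study treatment, could all place delivery inside it. The exclusion is therefore inferred. This stands too, but it leaves the published figure dependent on an unstated choice, which also needs settling.

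Separating vector from surgical causality is a legitimate choice, and protocol 8.4.2 does not require a pooled category. Agreed: the separate rows should stay. The combined row adds to them, and the SAP already accepts the combination for AESIs.

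The registries' requirements are not in the documents, so they may prescribe the narrow term. That is a fair limit, and the fix allows for it.

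Two further inferences should be resisted. The fellow-eye restriction does not conceal harm to the operated eye, because GT005 and the surgery go to the study eye only. It is also not a proven departure from the protocol: section 9.4.3 asks for ocular events by eye and for AEs by relationship, but not for the cross-classification by PT. Nor does the roughly 40% cataract-extraction figure in protocol 8.3 measure the gap. It is a published rate after vitrectomy, not a rate of SAEs judged surgery-related here, and surgery-related AEs already have their own table.

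**Conclusion.** The point holds for two outputs. On the consistent reading of SAP 2.7.1, the registry's related-SAE subset and the count of deaths from related SAEs leave out events attributed to the operation alone. This conflicts with the protocol's definition of related, with the treatment named in the estimand, and with the SAP's own handling of AESIs. No planned table gives the number of subjects with an AE or SAE related to either cause.

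The size is unknown. It equals the number of subjects whose related SAEs are all attributed to surgery only, which may be zero. The documents give no rates by cause, and the SAP reports that the study is being terminated early, so the planned sample size is no guide either. The conclusion rests on one assumption, that *study treatment* in these two outputs has the same meaning as in the rest of 2.7.1.

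The fellow-eye restriction is a separate, minor reporting gap. This is an inexpensive improvement to reporting and does not affect the efficacy analysis.

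**What to change.** In SAP 2.7.1:

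1. State what *study treatment* covers when causality is reported.
2. In the registry SAE table and the related-death count, define related as *study treatment and/or surgical procedure*, matching 2.7.1.1. If the registry format requires the narrow term, keep it and give procedure-related SAEs and deaths their own line.
3. Add two rows to the overall summary, any AE and any SAE related to study treatment and/or surgical procedure. Keep the existing separate rows.
4. As a minor separate change, add the fellow eye to the four related-event tables, or give the reason for leaving it out.

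No new data are needed. Protocol 8.4.2 and 8.6 have investigators assess causality for both the IMP and the surgical procedure and record it on the eCRF. The cost is SAP wording and a few table rows. The related-SAE figure for GT005 may become less favourable, by an amount that cannot be predicted from the documents.
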